7.2 List of pharmacodynamical parameters

To evaluate PD parameters of the drugs based on the data obtained on the concentration of soluble IL-6 receptor, as well as CRP level in the blood of volunteers, the following pharmacokinetic parameters will be calculated: the area under the "concentration-time" curve (AUC from the moment of administration of the drug to 1680 h (71 days after administration) and $AUC_{0-\infty}$ (to infinity), the maximum concentrations of the aforementioned markers in human serum, C_{max} , time to achieve maximum concentration, T_{max} (C_{min} and T_{min} for C-reactive protein) following a single-dose subcutaneous administration of the test drug. The values of the C_{max} and T_{max} will be calculated as the highest of the measured concentration values and the corresponding time of the observed maximum. The values of the C_{min} and T_{min} will be calculated as the lowest of the measured concentration values and the corresponding time of the observed minimum. The $AUC_{(0-t)}$ will be calculated using the logarithmic trapezoid method. The value of $AUC_{(0-\infty)}$ will be determined by the formula: $AUC_{(0-\infty)} = AUC_t + C_t / k_{el}$, where AUC_t is the area under the "concentration-time" curve from the moment of drug administration to the last measured CRP, IL-6 and sIL-6R concentrations (in this study it is $AUC_{(0-1680h)}$), C_t and k_{el} are the calculated values of the drug concentration in the last sample (in this study – C_{1680h}) and the elimination constants, respectively. To calculate C_t and k_{el} , the final (monoexponential) section of the pharmacokinetic curve is described using nonlinear regression analysis.

Thus, the main PD parameters evaluated will include:

1. C-reactive protein concentration determination:

Primary:

- ✓ AUC_{0-1680} (area under the concentration-time curve from the administration of the drug to 1680 h (71 days after administration) and $AUC_{0-\infty}$ (to infinity).

Secondary:

- ✓ C_{min} (minimum detectable concentration in blood serum),
- ✓ T_{min} (time to minimum serum concentration).

2. Determination of IL-6 concentration, soluble IL-6 receptor concentration:

Primary:

Translated from Russian to English, dated 06-Jul-2020

- ✓ AUC_{0-1680} (area under the concentration-time curve from the administration of the drug to 1680 h (71 days after administration) and $AUC_{0-\infty}$ (to infinity).

Secondary:

- ✓ C_{max} (maximum concentration in serum),
- ✓ T_{max} (time to maximum serum concentration).

Based on the results of flow cytometry, the following parameters will be calculated (a pilot study, it is not the endpoint)

- ✓ Percentage of occupancy of IL-6 receptors with BCD-089 2 hours after drug administration, as well as in 168, 336 and 504 hours.

[REDACTED]

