	
 ✓ AUC_{0-1680} (area under the concentration-time curve from the administration of the drug to 1680 h (71 days after administration) and $AUC_{0-\infty}$ (to infinity). 
Secondary:
 
 ✓ C_{min} (minimum detectable concentration in blood serum), ✓ T_{min} (time to minimum serum concentration). 
2. Determination of IL-6 concentration:
 
Primary:
 
 ✓ AUC_{0-1680} (area under the concentration-time curve from the administration of the drug to 1680 h (71 days after administration) and $AUC_{0-\infty}$ (to infinity). 
Secondary:
 
 ✓ C_{max} (maximum concentration in serum), ✓ T_{max} (time to maximum serum concentration). 
3. Determination of soluble IL-6 receptor concentration:
 
Primary:
 
 ✓ AUC_{0-1680} (area under the concentration-time curve from the administration of the drug to 1680 h (71 days after administration) and $AUC_{0-\infty}$ (to infinity). 
Secondary:
 
 ✓ C_{max} (maximum concentration in serum), ✓ T_{max} (time to maximum serum concentration). 
It will be additionally calculated within the study of pharmacodynamics based on the results of flow cytometry:
 
 ✓ Percentage of occupancy of membrane IL-6 receptors with BCD-089 2 hours after drug administration, 168, 336 and 504 hours after single injection¹
Pain assessment endpoint	
 ✓ The mean pain score during the injection on the visual analogue scale.
Safety endpoints:	
 ✓ Proportion of subjects who developed SAEs in each cohort. ✓ Proportion of subjects who developed AEs in each cohort.

¹ Given parameter is not an endpoint in the study.

Translated from Russian to English, dated 06-Jul-2020

	
 ✓ Proportion of subjects who developed local reactions in each cohort. ✓ Proportion of subjects who developed grade 3-4 AEs and SAE in each cohort. ✓ Proportion of subjects who developed any grade neutropenia in each cohort. ✓ Proportion of subjects who discontinued the study due to AEs and SAEs in each cohort. 																																

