2.2. Study Objectives

1. To determine the safe dose range of BCD-089, which will subsequently be used in the phase II clinical study;
2. To determine the proportion of study participants in whom a single subcutaneous administration of BCD-089 was accompanied by the development of adverse events, including the proportion of volunteers with neutropenia of varying severity;

Translated from Russian to English, dated 06-Jul-2020

3. To determine the main pharmacokinetic parameters (AUC_{0-1680} , $AUC_{0-\infty}$, C_{max} , T_{max} , $T_{1/2}$, K_{el} and CL) of BCD-089 after a single subcutaneous injection in increasing doses to healthy volunteers;
4. To determine the main pharmacodynamic parameters (C_{max} , T_{max} , C_{min} , T_{min} , AUC_{0-1680}) for C-reactive protein, IL-6 and soluble receptor IL-6;
5. To determine the proportion of volunteers, in whom binding and/or neutralizing antibodies to BCD-089 were determined following its single administration.

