9.1.2. Pharmacodynamical parameters

Based on the obtained concentrations of C-reactive protein, IL-6 and soluble IL-6 receptor in the blood of each volunteer, the following pharmacodynamic parameters will be calculated at the Protocol-specified time intervals:

1. C_{\max} – maximum blood concentration of C-reactive protein, IL-6 and soluble IL-6 receptor over the observation period.
2. t_{\max} – time to maximum blood concentration (C_{\max}) of C-reactive protein, IL-6 and soluble IL-6 receptor.
3. AUC_{0-1680} – the area under the concentration-time curve for C-reactive protein, IL-6 and soluble IL-6 receptor over the time interval from 0 to 1680 hours. AUC_{0-1680} is calculated using the trapezoidal method with the following formula:

$$AUC_{0-1680} = \sum_{p=2}^{16} \frac{(C_p + C_{p-1}) * (t_p - t_{p-1})}{2},$$

where C_p concentration of C – reactive protein, IL – 6 and soluble IL
– 6 receptor values

ИЛ6 in the blood at t moment of time t_p (hours),

$$t_p \in \{0; 2; 8; 12; 24; 48; 72; 96; 120; 168; 240; 336; 504; 672; 1176; 1680\}_{p=1, \dots, 16}$$

4. C_{\min} – minimum blood concentration of C-reactive protein, IL-6 and soluble IL-6 receptor over the observation period.
5. t_{\min} – time to minimum blood concentration (C_{\min}) of C-reactive protein, IL-6 and soluble IL-6 receptor.

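### AUC0-∞ is listed as a primary quantity for CRP, IL-6 and sIL-6R, but its only visible formula is carried over from the drug PK without baseline correction, and objective 4 and section 9.1.2 provide only AUC0-1680

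*Combined protocol and SAP*

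**What the plan says.** **Listed as primary.** For each marker, the synopsis, 4.1.2 and 7.2 give as primary the "area under the concentration-time curve from the administration of the drug to 1680 h (71 days after administration) and" the area to infinity.

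**Not in the objective or in section 9.** Objective 4 (synopsis and 2.2) begins "To determine the main pharmacodynamic parameters" and names Cmax, Tmax, Cmin, Tmin and AUC0-1680. Section 9.1.2 defines the same five quantities and no area to infinity. Section 9.1.1 defines AUC0-∞ for the antibody only.

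**The formula.** Only 7.2 gives one for the markers: AUC0-∞ = AUC_t + C_t/k_el. AUC_t is the marker area, taken "from the moment of drug administration to the last measured CRP, IL-6 and sIL-6R concentrations". The surrounding text is the PK text of 7.1:
- it introduces the markers with "concentration of soluble IL-6 receptor, as well as CRP level in the blood of volunteers, the following pharmacokinetic parameters will be calculated";
- C_t and k_el "are the calculated values of the drug concentration in the last sample" and the elimination constants;
- they are obtained where "the final (monoexponential) section of the pharmacokinetic curve is described using nonlinear regression analysis".

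**Two related points.** In 7.2 the area to time t "will be calculated using the logarithmic trapezoid method", whereas in 9.1.2 AUC0-1680 "is calculated using the trapezoidal method with the following formula", and the formula written there is the linear one. Section 9.2 (Statistical analysis methods) lists clearance and an elimination constant under pharmacodynamics, although the markers are not dosed.

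**The concern.** The term C_t/k_el is the area under a curve that falls mono-exponentially to zero. That suits an antibody that is cleared. CRP, IL-6 and sIL-6R are produced by the body. If a marker settles at a positive level after the drug has gone, its area grows without limit as the horizon is extended, and there is no true value for the formula to estimate.

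Support for a positive baseline differs by marker. For sIL-6R it is documented: section 1.1 says the soluble receptor is present in all body fluids. For CRP it is implied by the Cmin and Tmin endpoints. For IL-6 it is an assumption.

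At stake is one of the two areas listed as primary for each marker. It would be missing, or would depend on choices the visible plan leaves to the analyst. Section 9.2 also lists PD area under the curve among the quantitative data to be compared by tests, without saying which area.

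**Working it through.** The documents state no numerical value for a marker AUC0-∞, so there is no plan figure to reproduce. The check has a textual and a numerical part.

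**1. Literal reading of 7.2.** AUC_t is in marker concentration × hours. C_t/k_el, as defined, is in drug concentration × hours. The sum is not an area of either substance. Everything below therefore substitutes the marker's own C_t and k_el, which is the reading most favourable to 7.2.

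**2. Inputs.** The times are the protocol's 16 points (9.1.2): 0, 2, 8, 12, 24, 48, 72, 96, 120, 168, 240, 336, 504, 672, 1176, 1680 h. The documents give no marker levels, so every profile is an assumption with baseline = 1. Following 7.2, I use the log trapezoid and fit A·exp(−k·t) by nonlinear least squares to the last n points, with fitted C_t.

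**3. Rising marker.** C(t) = 1 + A·[exp(−t/τ) − exp(−t/60)], with A = (peak − 1)/m, where m is the maximum of the bracket.

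*3-fold peak, τ = 300 h.* m = 0.535, so A = 2/0.535 = 3.738. AUC0-1680 = 2595.1.

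| Terminal points | C_t | k_el (1/h) | C_t/k_el | Ratio to AUC0-1680 |
|---|---|---|---|---|
| 3 | 0.969 | 0.000341 | 2841 | 2.09 |
| 4 | 0.926 | 0.000466 | 1987 | 1.77 |
| 5 | 0.825 | 0.000657 | 1256 | 1.48 |

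The true above-baseline area after 1680 h is 3.738 × [300·exp(−5.6) − 60·exp(−28)] = 4.15, and 4.15/2595.1 = 0.2%. The formula adds 48% to 109%, almost all of it baseline.

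*Other profiles.* A 2.1-fold peak with τ = 300 h gives 3.29, 2.60 and 2.07 times AUC0-1680. A 10-fold peak with τ = 600 h gives 1.18, 1.17 and 1.15, against a true tail of 5.7%. The distortion shrinks as the response grows relative to baseline.

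*Divergence.* For the 3-fold, 300 h marker the exact area to 1680, 3360, 6720 and 16,800 h is 2573, 4257, 7617 and 17,697. It does not converge.

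**4. Suppressed and recovering marker (CRP-like).** C = 1 at time 0, 0.1 up to 504 h, then 1 − 0.9·0.5^((t − 504)/168). Values at 504, 672, 1176 and 1680 h are 0.10, 0.55, 0.944 and 0.993. The last limb rises, so it contains no elimination phase and k_el cannot be estimated as an elimination constant. The last limb also rises in all nine combinations of suppression to 336, 504 or 672 h with recovery half-time 84, 168 or 336 h.

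**5. The other k_el in the documents.** Section 9.1.1 sets k_el = 1/MRT, for PK only. On the profile in step 4, linear AUC0-1680 = 970.4 and AUMC0-1680 = 1,120,868, so MRT = 1155.1 h. AUC0-∞ = 970.4 + 0.993 × 1155.1 ≈ 2117, or 2.2 times AUC0-1680. A marker that never moves from 1 has MRT = 840 h and gives 1680 + 840 = 2520, or 1.5 times AUC0-1680. That factor reflects only the observation window.

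**6. Trapezoid rule.** On the profile in step 4, AUC0-1680 is 950.8 (log) or 970.4 (linear), a gap of 2.0%. Over the nine combinations the log value is 1.2% to 2.4% lower in six and 7.1% to 9.4% lower in the three with suppression to 672 h.

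**7. With baseline subtracted.** The 7.2 formula then gives 892.4, 892.4 and 892.6 for the 3-fold, 300 h marker, against a true 897.2. For 10-fold, 600 h it gives 6954, 6955 and 6962, against 6974.

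**The case against.** **Redaction.** Sections 4.6.3.6.2 to 4.6.3.6.4 (marker assays), the block that closes 7.2, and 9.5 (missing and non-evaluable data) are blacked out. They could hold a rule for a non-estimable k_el or a baseline correction. The first would only explain missing values. The second would matter: step 7 shows that the extrapolation then works for a rising marker. A reader might infer that a marker AUC0-∞ is meaningless under any rule. The documents do not support that; the criticism covers the visible, uncorrected text.

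**Negative areas.** A reader might infer that the plan will produce negative CRP areas. Forcing the fit on the rising limb in step 4 does give −1158, −291 and −127 with 3, 4 and 5 points. But 7.2 calls for a final mono-exponential section, and a rising limb offers no elimination phase, so no estimate is the likelier outcome. The 1/MRT definition gives +2117 on the same profile. The sign depends on the reading.

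**Low impact.** The hypothesis in section 3 concerns the maximum tolerated dose, the sample size follows the 3+3 design, and escalation rests on 7-day DLTs. This stands. A reader might infer that the PD comparisons in 9.2 will use AUC0-∞; the text neither includes nor excludes it, and 9.1.2 defines only one PD area.

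**Assumed baselines.** These are documented for sIL-6R only. The point is worded conditionally for that reason.

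**Conclusion.** The point holds for the text that can be read. The endpoint lists make AUC0-∞ primary for three markers, while objective 4 and 9.1.2 leave it out. The one visible formula either mixes drug and marker or, with marker values and no baseline correction, has no finite target once the marker returns to a positive baseline.

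Under the assumed rising profiles the result lies between 1.15 and 3.29 times AUC0-1680, and for a modest response it moves strongly with the number of terminal points. For a suppressed CRP there is no elimination phase to fit. None of these figures is an expected value for this trial.

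The consequence is confined to reported PD results. AUC0-1680 does not use the extrapolation, and dose escalation does not use PD. It should be fixed, but it is no threat to the study's safety decisions.

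**What to change.** - Delete AUC0-∞ and the C_t/k_el extrapolation for CRP, IL-6 and sIL-6R from the synopsis, 4.1.2 and 7.2.
- Delete clearance and elimination constant from the pharmacodynamics list in 9.2.
- Keep AUC0-1680 as the primary PD area, in line with objective 4 and 9.1.2.
- State one trapezoid rule in both 7.2 and 9.1.2. The choice is the sponsor's.
- Optional: add a supportive baseline-adjusted AUC0-1680, using the pre-dose sample that 9.7 already requires for the PD analysis.

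The cost is protocol and SAP wording, with no new data or sampling. The downside is that one listed endpoint is dropped. If the redacted text already holds a baseline correction and the sponsor wishes to keep an extrapolated area for a rising marker, 7.2 and 9.1.2 would have to state that correction and define C_t and k_el from the marker.

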8. SAFETY ASSESSMENT

List of safety parameters

To assess the safety of the study therapy, the following parameters (secondary endpoints) will be used:

- ✓ Proportion of subjects who developed SAEs in each cohort.
- ✓ Proportion of subjects who developed AEs in each cohort.
- ✓ Proportion of subjects who developed injection site reactions in each cohort.
- ✓ Proportion of subjects who developed grade 3-4 AEs in each cohort.
- ✓ Proportion of subjects who developed any grade neutropenia in each cohort.
- ✓ Proportion of subjects who discontinued the study due to AEs and SAEs in each cohort.

Translated from Russian to English, dated 06-Jul-2020

8.2 Definitions

8.2.1 Adverse Events

Adverse event (AE): Any untoward medical event occurring in a participant of a clinical study after the administration of a medicinal product, which can have no causal relationship with the administration of the drug.

[figure not shown]
An AE is any untoward and unintended sign (including an abnormal laboratory finding), symptom, or disease, the time of occurrence of which does not exclude a causal relationship with the use of the drug, regardless of whether it is related or not, from the start of the study drug administration until day 28 inclusive after withdrawal of the volunteer from the clinical study.

As part of this study, the Investigator had to register all AEs, starting from grade 1 according to the classification, regardless of their clinical significance.

8.2.2 Serious adverse events

Serious adverse event (SAE) is any untoward medical event, regardless of the dose of the drug:

- Results in death;
- is life-threatening;
- requires hospitalization or prolongation of existing hospitalization;
- results in persistent or significant disability/incapacity;
- is a congenital anomaly or birth defect.

Translated from Russian to English, dated 06-Jul-2020

[REDACTED]

8.3 Methods and timeframes for the assessment, recording, and analysis of safety parameters

8.3.1 Timeframes for the assessment of safety parameters

Information about serious adverse events will include data on SAEs occurring from the moment of signing the ICF and until the patient stops participating in the study (as planned or prematurely). Information about AEs not meeting the seriousness criteria will be registered from the first administration of the drug and until the volunteer stops participating in the study (as planned or prematurely).

Information about all SAEs will be reviewed immediately starting from the submission of SAE report to the Drug Safety Division of JSC BIOCAD (provided timely notification of the

Translated from Russian to English, dated 06-Jul-2020

Investigator in case of SAEs). A pooled analysis of SAEs will be carried out during the preparation of the final study report.

AEs not meeting the seriousness criteria will be analyzed routinely during the preparation of the final study report.

8.3.2 Methods and timeframes for the assessment and registration of safety parameters

Safety analysis will include all volunteers who received the test drug. Cases of SAEs that developed before the test drug administration should also be analyzed.

Safety analysis will be based on:

- data on reported AEs and SAEs;
- physical examination data and vital signs assessment;
- complete blood count, blood chemistry, and urinalysis results;
- electrocardiography results;
- data on cases of injection site reactions.

The frequency of these procedures throughout the study is described in Section 4.6.1 “The schedule of study visits and procedures”. AE/SAE are registered according to the guidance provided by the Sponsor.

The Investigator is responsible for registering the adverse events reported in clinical studies.

AE are registered from the moment of signing the informed consent form and until the volunteer completes his participation in the study (as planned or prematurely). SAEs are registered from the moment of signing the informed consent and until the patient stops participating in the study (as planned or prematurely) as well as for a longer period after the last dosing, if the Investigator believes that this SAE is associated with the use of the drug or any study procedures.

Adverse events (AEs) that do not meet the seriousness criteria are registered by the Investigator in source documents and in the CRF and the records are provided to the clinical study monitor at the next scheduled monitoring visit for evaluation. Serious adverse events (SAEs) must be promptly reported to the Sponsor, within 24 hours.

[REDACTED]

[REDACTED]

[REDACTED]

Translated from Russian to English, dated 06-Jul-2020

[REDACTED]

8.4 Requirements for reports, AE registration and reporting procedures, and AE Reporting Form completion

8.4.1 AE/SAE registration

Presence or absence of adverse events during the period from the last visit is evaluated at each visit. Any serious adverse event observed in a volunteer from signing the informed consent form should be registered in source documents and in the dedicated Adverse Event Reporting Form (in eCRF).

Adverse events are registered and numbered consecutively, as they occur. Each AE is reported using the AE Reporting Form. The rules for AE/SAE reporting are described in detail in the Guidance provided by the Sponsor.

Adverse events are registered regardless of seriousness or causal relationship with study therapy. **All AEs are subject to recording in the study, including Grade 1 AEs (CTCAE v.4.03).** If the same adverse event reoccurs (after the previous case resolved), it should be registered as a new adverse event, with a separate number.

8.4.2 AE/SAE Reporting Form completion

[REDACTED]

Translated from Russian to English, dated 06-Jul-2020

[Redacted content]

Translated from Russian to English, dated 06-Jul-2020

[REDACTED]

Translated from Russian to English, dated 06-Jul-2020

Information about the method and duration of subjects' follow-up after an AE/SAE

If a volunteer is discontinued from the study due to an AE/SAE, the Investigator should continue his/her management and follow-up in accordance with the standard practices used at the study site for AE/SAE treatment. The volunteer will be followed up until full resolution of the AE or SAE. See Section 5.4 for further details.

9. STATISTICAL METHODS

9.1 Calculation of the parameters of pharmacokinetics and pharmacodynamics

9.1.1. Pharmacokinetic parameters

Based on the calculated concentration values for the anti-IL-6 monoclonal antibody in the blood of each volunteer, the following pharmacokinetic variables will be estimated at time points specified in this protocol:

1. C_{\max} - maximum serum concentration of anti-IL-6 receptor antibody over the observation period.
2. t_{\max} - time to achieve maximum serum concentration (C_{\max}) of anti-IL-6 receptor antibody.
3. AUC_{0-1680} — the area under the concentration of anti-IL-6 receptor monoclonal antibody-time curve over the time interval from 0 to 1680 hours. AUC_{0-1680} will be calculated using the trapezoid method using the following formula, where C_p is the concentration of the drug BCD-089 in the blood at the time t_p in hours:

$$t_p \in \{0; 2; 8; 12; 24; 48; 72; 96; 120; 168; 240; 336; 504; 672; 1176; 1680\}_{p=1, \dots, 16}$$

4. $AUMC_{0-1680}$ - total area under the curve of the concentration of anti-IL-6 receptor monoclonal antibody multiplied by time over the time interval from 0 to 1680 hours. $AUMC_{0-1680}$ will be calculated using the following formula:

$$AUMC_{0-1680} = \sum_{p=2}^{16} \frac{(C_p * t_p + C_{p-1} * t_{p-1}) * (t_p - t_{p-1})}{2},$$

where C_p — concentration of anti – IL – 6

– receptor monoclonal antibody против рецептора ИЛ6

Translated from Russian to English, dated 06-Jul-2020

in the blood at t_p

$$t_p \in \{0; 2; 8; 12; 24; 48; 72; 96; 120; 168; 240; 336; 504; 672; 1176; 1680\}_{p=1, \dots, 16}$$

5. **Total clearance (Cl)** is a parameter that reflects the volume of test tissue, which is cleared from the anti-IL-6 receptor monoclonal antibody per unit of time and is determined by the ratio of the anti-IL-6 receptor monoclonal antibody dose (*DOSE*) to $AUC_{(0-1680)}$:

$$CL = \frac{DOSE}{AUC_{0-1680}}$$

6. **Mean residence time (MRT)** of the anti-IL-6 receptor monoclonal antibody molecule in the body will be calculated as the ratio of $AUMC_{0-1680}$ to AUC_{0-1680} :

$$MRT = \frac{AUMC_{0-1680}}{AUC_{0-1680}}$$

7. **Elimination constant** of the anti-IL-6 receptor monoclonal antibody (k_{el}) will be determined using the following formula:

$$k_{el} = \frac{1}{MRT}$$

8. **Half-life period** of the anti-IL-6 receptor monoclonal antibody ($T_{1/2}$) will be determined using the following formula:

$$T_{1/2} = \frac{\ln(2)}{k_{el}} = \ln(2) * MRT$$

9. **The area under the concentration-time curve** for anti-IL-6 receptor monoclonal antibody **over the time interval from 0 to ∞ ($AUC_{0-\infty}$)**.

$$AUC_{0-\infty} = AUC_{0-1680} + \frac{C_{1680}}{k_{el}}, \text{ where}$$

Translated from Russian to English, dated 06-Jul-2020

C_{1680} – concentration of anti-IL-6 receptor antibody over the period equal to 1680 hours after the drug administration.

